11.5 Please provide a justification for your sample size

The primary outcome variable for this research study binary (successfully stop the pulse: yes/no) and we conducted a power analysis for a parallel group non-inferiority trial. Assuming the two arms have the same high successful rate, with 80% power, and define the non-inferiority limit as 10% (so that a difference bigger than this would matter in practice), we estimated sample size required for each group is 13 applications (at least), so a total sample size of 26 applications (at least). Given the potential missing data and to ensure we will have enough statistical power for the final analyses, we will set the total sample size of 40 applications for this study. Since the tourniquet will be applied to participants' both legs (not at the same time), each leg will be one application and one participant will be able to fulfill two applications. As such, we will recruit no more than 20 participants for the study session and one additional participant for the training session.

11.6 Data Analysis Plan: Complete description: Background, Objectives, Design, Step by Step how the project is going to be done, Data analysis plan:

Given that the primary study outcome variable is binary, we will use a chi-square test for the analysis. Descriptive statistics will be used to describe other study variables, including participants' demographic information.

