In January 2020, the research team conducted a pilot study to evaluate this novel layperson tourniquet in a community lay public sample recruited from at the NBC Health Expo in Washington, DC. Findings of this pilot study were promising. One highlight of the results was that the proportion of participants who applied the tourniquet correctly using the layperson tourniquet was significantly higher than that using the CAT (93.3% versus 6.3%). Moreover, for when asked about their favoritism toward the tourniquet, 93.3% favored the novel layperson tourniquet, whereas 68.8% favored the CAT.

In addition to research results, feedback provided by the participants in this pilot study allowed the research team and the manufacturing partner to make adjustments and improvements to the testing device. Now we have completed a pilot study evaluating overall user experience of the novel layperson tourniquet, our next step is to conduct a functionality study examining the function of this novel layperson tourniquet and to see if it performs on par with the CAT.

9.3 Objectives/Specific Aims/Research Questions:

Describe the purpose and objective(s) of the study, specific aims, and/or research questions /hypotheses

The objective of the study is to determine if the novel layperson tourniquet (SMART TQ)'s ability to occlude arterial blood flow is non-inferior to a Combat Application Tourniquet (CAT).

9.4 Study Design:

Describe study design in one to two sentences (e.g., prospective, use of existing records/data /specimens, observational, cross-sectional, interventional, randomized, placebo-controlled, cohort, etc.). Specify the phase – Phase I, II, III, or IV – for FDA-regulated investigational drug research

This study will be a single blinded, randomized clinical trial.

9.5 Target Population:

Describe the population to whom the study findings will be generalized

The study will benefit the general public.

9.6 Benefit to the DoD:

State how this study will impact or be of benefit to the Department of Defense

Research findings and information collected from this research study would help ongoing efforts of developing a layperson tourniquet.

10.0

Study Procedures, Data Management, and Privacy

10.1 Study Procedures:

Describe step-by-step how the study will be conducted from beginning to end

This study will be a single blinded, randomized clinical trial. The study will be conducted in a room at USU's Multidisciplinary Laboratories.

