- To capture the baseline dorsalis pedis (DP) pulse: A blinded observer uses a doppler ultrasound to check DP pulse, the artery pulse on the surface of the foot. Doppler ultrasound is a small medical ultrasound machine that uses high-frequency sound waves to measure the amount of blood flow through the arteries and veins. The doppler ultrasound probe will be placed on the exposed foot, a pulse detected, and the location where the pulse is detected on that foot will be marked with an "X" using a surgical marker, and the doppler probed removed. This marked location will be where the doppler probe is placed later to determine whether there is a pulse.
- The research team member will measure the circumference of the leg at the area of tourniquet application. To keep the application location consistent across all the participants, we will mark where on the leg the tourniquet should be placed for each application.
- A medical professional records which leg will be used for tourniquet application (left leg or right leg)
- The medical professional applies the tourniquet. This is the first application of the tourniquet. *For tourniquet application, in order to signal medical professional stops tourniquet application (i.e., stops tightening the tourniquet), the doppler signals will be audible to medical professionals. Once the doppler signals stop, the medical professionals will stop applying/tightening the tourniquet.*
- Upon the completion of the tourniquet application, the blinded observer records the presence or absence of a dopplerable pulse. A blinded observer again uses a doppler ultrasound probe to check the dorsalis pedis (DP) pulse, the artery pulse on the surface of the foot, at the previously marked "X" location on the foot.
- The medical professional removes the tourniquet and the study participant takes a break.
- The medical professional places a blood pressure cuff first and then places a tourniquet over the blood pressure cuff. This is the second application of the tourniquet. The blood pressure cuff will be attached to a fluid (e.g., water)

pressure sensor to measure surface pressure under the tourniquet. The medical professional will tighten the tourniquet until the doppler pulse is eliminated. The medical professional will then read and record the pressure readings.

- **The medical professional removes the tourniquet.**

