The procedures will then be repeated to a participant's other leg for the other arm. For example, if a participant is initially assigned to the CAT and uses the right leg for tourniquet application. The participant will then be in the SMART TQ arm for the left leg.

Termination Procedures

For the first tourniquet application on each leg, the observer will use doppler ultrasound to assess the participant's foot for a present or absent dorsalis pedis pulse. The observer will make the assessment at the location previously marked with a surgical marker. As soon as the pulse is determined to be present or absent, the observer will verbally tell the medical professional, "remove the tourniquet now."

For the second tourniquet application on each leg, the medical professional will tighten the tourniquet on top of the neonatal blood pressure cuff as described. The study team member will record the pressure. As soon as the pressure is noted, the study team member will tell the medical professional, "remove the tourniquet now."

Participant Post-study Assessment

Following the application of two tourniquets to both legs, the study team will ask the participant to rest while lying on the table for five minutes. After five minutes, the study team member will ask the participant the following questions:

- Do you have any persistent pain beyond mild aching at the application site?
- Do you have numbness, tingling, or other abnormal sensations?
- Does your leg feel weak?

If the answer is yes to any question, the team member will ask the participant to rest for five more minutes and re-ask the questions. If the answer to any question is still yes, the study team member will recommend that the participant seek medical care at an emergency department or with the participant's physician. If the study team member or participant is concerned that they are experiencing a medical emergency, they will call 9-1-1 and alert any of the medical professionals assisting with the study for assistance.

If the answer to the questions is no, the study team member will ask the participant to walk up and down the hall in the MDL. The study team member will observe the participant ambulating. If the person feels normal while walking, they can be discharged from the study.

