11.0 Statistical/Data Analysis Plan

11.1 Statistical Considerations:

List the statistical methods to be used to address the primary and secondary objectives, specific aims, and/or research hypotheses. Explain how missing data and outliers will be handled in the analysis. The analysis plan should be consistent with the study objectives. Include any sub-group analyses (e.g., gender or age group). Specify statistical methods and variables for each analysis. Describe how confounding variables will be controlled in the data analysis

The primary outcome variable for this research study binary (successfully stop the pulse: yes/no) and we conducted a power analysis for a parallel group non-inferiority trial. Assuming the two arms have the same high successful rate, with 80% power, and define the non-inferiority limit as 10% (so that a difference bigger than this would matter in practice), we estimated sample size required for each group is 13 applications (at least), so a total sample size of 26 applications (at least). Given the potential missing data and to ensure we will have enough statistical power for the final analyses, we will set the total sample size of 40 applications for this study. Since the tourniquet will be applied to participants' both legs (not at the same time), each leg will be one application and one participant will be able to fulfill two applications. As such, we will recruit no more than 20 participants for the study session and one additional participant for the training session.

11.2 Sample Size:

A total of 21 participants will be recruited. We will recruit no more than 20 participants that allow us to complete 40 applications, with 20 applications in each arm. We will recruit one additional participant for the training session.

11.3 Total number of subjects requested (including records and specimens):

21

11.4 If you are recruiting by study arm, please identify the arms of the study and how many subjects will be enrolled in each arm

We will recruit no more than 10 participants (20 applications) for each study arm.

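### The objective is non-inferiority with a 10% limit, but the only planned primary analysis is a chi-square test that never uses the limit

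*Combined protocol and SAP*

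**What the plan says.** Section 9.3 gives a single objective: to determine whether the SMART TQ's "ability to occlude arterial blood flow is non-inferior to a Combat Application Tourniquet (CAT"). Sections 11.1 and 11.5 size the trial as a parallel-group non-inferiority comparison: "Assuming the two arms have the same high successful rate, with 80% power", and they "define the non-inferiority limit as 10% (so that a difference bigger than this would matter in practice"). The result is at least 13 applications per group, raised to 40 in total (20 per arm).

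Section 11.6 holds the whole primary analysis: "Given that the primary study outcome variable is binary, we will use a chi-square test for the analysis". Other variables are described only. The form's instruction in 11.1 reads: "The analysis plan should be consistent with the study objectives".

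Two design features in section 10.1 bear on the analysis. Each participant receives both devices: "The procedures will then be repeated to a participant's other leg for the other arm". Tightening is guided by the outcome signal: "Once the doppler signals stop, the medical professionals will stop applying/tightening the tourniquet". Section 11.4, however, describes the arms this way: "We will recruit no more than 10 participants (20 applications) for each study arm".

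**The concern.** A chi-square test, as naturally read, asks whether two proportions differ. The 10% limit plays no part in it. A significant result would show a difference, not whether it exceeds 10 points; a non-significant result would show neither equality nor non-inferiority. The limit is used only for sizing, and nothing in 11.1 to 11.6 carries it into the analysis.

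The plan does not say that a non-significant result will be reported as non-inferiority, but it offers no other route to its objective and does not exclude that reading. Because tightening continues until the signal stops, occlusion rates near 100% in both arms are plausible. There the chi-square is least informative, or cannot be computed.

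A lesser problem is that the ordinary chi-square treats the 40 applications as independent, although they form 20 within-person pairs.

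**Working it through.** **Inputs.** From the documents: limit 10% (taken as percentage points, since the scale is not stated), power 80%, equal high success rates, 13 per group, 20 applications per arm, both devices on each participant. Not in the documents and assumed here: alpha (one-sided 5% or 2.5% for non-inferiority, two-sided 0.05 for the chi-square) and success rates (95% or 99%, and lower for SMART TQ where shown).

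**1. The plan's own figure.** The normal approximation is n per arm = (z_alpha + 0.842)² × 2p(1−p) / 0.10². With p = 0.99 and one-sided 5%: (1.645 + 0.842)² × 0.0198 / 0.01 = 12.2, which rounds up to 13. At one-sided 2.5% the same rate gives 15.5, so 16. The 13 is thus reproduced by a non-inferiority formula with about 99% success. A chi-square superiority calculation for a 10-point difference needs 69 or more per group.

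**2. What the chi-square does at 20 per arm** (uncorrected). For CAT 20/20 and SMART TQ 17/20: 40 × (17×0 − 3×20)² / (20 × 20 × 37 × 3) = 144,000 / 44,400 = 3.24, p = 0.072. The paired McNemar test on the same split (3 CAT-only pairs, 0 SMART-only) gives 3²/3 = 3, p = 0.083. At 16/20 the chi-square gives p = 0.035.

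Exact enumeration, applications taken as independent:

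| True CAT / SMART TQ | Non-significant | Undefined | Total |
|---|---|---|---|
| 99% / 89% | 77.8% | 8.0% | 85.7% |
| 99% / 84% | 63.3% | 2.5% | 65.7% |
| 95% / 85% | 83.3% | 1.4% | 84.6% |

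The totals come from unrounded values. In all three rows SMART TQ is at or beyond the limit. If both rates are equal, all 40 succeed with probability 0.99^40 = 0.67 or 0.95^40 = 0.13, and the statistic is then 0/0.

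**3. What an analysis against the limit gives with 20 pairs.** With no discordant pair, the Tango score lower limit is −z²/(n + z²):

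- one-sided 5%: −2.706/22.706 = −11.9 points
- one-sided 2.5%: −3.842/23.842 = −16.1 points

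An exact zero-failure bound, 1 − alpha^(1/20), gives −13.9 and −16.8 points. So 20/20 against 20/20 does not clear −10 by either method. A Wald interval for the same data collapses to 0 to 0 and would pass, so the choice of method decides the conclusion.

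Enumerating every outcome of 20 pairs, Tango passes only when SMART-only pairs outnumber CAT-only pairs. One against none gives −7.5 points at 5% and −11.9 at 2.5%; two against none gives −7.7 at 2.5%.

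**4. Power of 20 pairs by Tango**, equal rates, legs taken as independent:

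| Alpha (one-sided) | Both 99% | Both 95% |
|---|---|---|
| 5% | 15% | 27% |
| 2.5% | 1.4% | 10% |

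Power is higher at 95% because passing needs at least one CAT failure. By contrast, the approximation in step 1 at 20 per arm gives z = 0.10/√(0.0198/20) − 1.645 = 1.53, a power of 94%.

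**The case against.** The strongest reply is that this is under-specification rather than error. The limit is defined, a larger difference is said to matter in practice, and a reader could set the observed difference against it. The miss rates in step 2 are wrong conclusions only if someone reports a non-significant test as non-inferiority, which the plan never says. That condition is accepted, and those figures are illustrations. It does not rescue the plan: comparing a point estimate with a limit is not a test, and the one test named ignores the limit.

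Second, the power figures rest on an assumed alpha, rate and method, and on independent legs. They run from 1.4% to 94% and partly reflect discreteness: at 99% and one-sided 5%, Tango power is 16.9% with 24 pairs and 78.4% with 25. This stands. It means the loss of power must be stated conditionally, and it shows why the method should be fixed before the data are seen.

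Third, if all 40 succeed, the Tango interval does not show non-inferiority either. True, but it yields an estimate with stated uncertainty, where the chi-square yields nothing.

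Fourth, section 11.4 may mean that ten participants start in each arm. That is a fair reading; the wording is ambiguous rather than plainly contradictory, and pairing remains the lesser issue.

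**Conclusion.** The concern holds and must be fixed. Sections 11.1 to 11.6 are legible in full, and nothing in them applies the 10% limit to the data. Followed as written, the plan cannot answer its only stated question. This rests on the text alone and needs no assumption about rates.

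The size of the consequence does depend on assumptions. A 15-point observed deficit can be non-significant (p = 0.072). At 99% against 89%, the test would fail to flag the deficit, or be undefined, in about 86% of trials. By a paired score interval, 20 pairs give power of 1.4% to 27% over the alphas and rates considered, against the stated 80%. Non-inferiority would then be unlikely to be shown, though not impossible.

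**What to change.** 1. In 11.6, replace the chi-square with the SMART TQ minus CAT difference in occlusion rate and a confidence interval suited to paired proportions near 100% (for example Tango's score interval, or an exact method).
2. State alpha and its sidedness, and that the limit is in percentage points. Conclude non-inferiority only if the lower limit is above −10 points. State that a non-significant difference test is not evidence of non-inferiority.
3. Reconcile the parallel-group sizing in 11.1 and 11.5, and the arm description in 11.4, with section 10.1, where every participant has both devices.
4. Restate the power of 20 pairs under the chosen method and alpha, with the assumed success rate written down.

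**Cost.** Wording changes to 11.1, 11.4, 11.5 and 11.6, submitted as an ethics-board amendment, with no new data. The restated power will probably look much worse than 80%. At the cap of 20 participants the result may have to be reported mainly as an estimate with its interval.

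If the sample size is reopened, the method's error rate near 100% must be checked. For a failure-free result to pass, Tango needs 25 pairs at one-sided 5% (2.706/27.706 = 9.8 points) and 35 at 2.5% (3.842/38.842 = 9.9 points). The exact bound needs 29 pairs (0.9^29 = 0.047) and 36 (first n with 0.9^n below 0.025). At 25 pairs and one-sided 5%, Tango would falsely declare non-inferiority in 0.9^25 = 7.2% of trials if CAT were at 100% and SMART TQ at 90%.

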12.0 Participant Information

12.1 Subject Population:

The study population includes individuals with access to the USU campus and prior tourniquet experience (an individual has received tourniquet training previously or has used tourniquet before so that they would understand the discomfort when a tourniquet is applied).

12.2 Age Range:

Check all the boxes that apply. if the age range of potential subjects (specimens, records) does not match the range(s) selected, please specify in the text box.

- 0-17
- 18-24
- 25-34
- 35-44
- 45-54
- 55-64
- 65-74
- 75+

12.3 Gender:

- Male
- Female
- Other

12.4 Special categories, check all that apply

- Minors /Children
- Students
- Employees - Civilian
- Employees - Contractor
- Resident/trainee
- Cadets /Midshipmen
- Active Duty Military Personnel
- Wounded Warriors
- Economically Disadvantaged Persons
- Educationally Disadvantaged Persons
- Physically Challenged (Physical challenges include visual and/or auditory impairment)
- Persons with Impaired Decisional Capacity
- Prisoners
- Pregnant Women, Fetuses, and Neonates
- Non-English Speakers
- International Research involving Foreign Nationals - Headquarters Review is necessary

You must also consider the requirements of DoDI 3216.02, paragraph 7.e.

You must also consider the requirements of DoDI 3216.02, Enclosure 3, paragraph 7.e.

12.5 Inclusion Criteria:

Order Number	Criteria
1	Participants – Individuals with access to the USU campus and prior tourniquet experience

12.6 Exclusion Criteria:

Order Number	Criteria
1	Individuals younger than 18 years old or older than 65 years old
2	Individuals with the following conditions or history will be excluded from participation: hypertension, prior vascular surgery, peripheral vascular disease, diabetes, prior lower extremity vascular surgery, active lower extremity infection, any hypercoagulable condition (such as Factor V Leiden, or Protein C and S deficiency), pregnancy, or any condition in which the participant is concerned they may suffer harm from brief tourniquet application.
3	Individuals with any history of deep venous thrombosis or pulmonary embolism.

13.1 Please describe the recruitment process, including how subjects will be identified and selected for the study.

We will recruit 21 study participants, with 20 being study participants and one additional being the participant in the training session, from USU. We will obtain appropriate approvals to recruit participants. Recruitment will be conducted via passive methods, such as class announcements.

Individuals who are interested in this study can contact a member of the research team and the research team member will ask if the individual is able to complete the screening questions. Upon the completion of the screening questions, if eligible, participants' consent will be conducted in a private room or via private virtual method.

13.2 Compensation for Participation:

No compensation for participating in this research study.

13.3 Please describe the pre-screening process. If no pre-screening, enter Not Applicable in the text editor

The screening will be conducted virtually via a phone call. Once an individual expresses interest in this research study, the research team will proceed with the screening by calling the individual and asking the screening questions. We added this information to the revised protocol.

Screening Questions

1. How many times have you applied a tourniquet before?
2. Do you have any of the following conditions or history:

hypertension, prior vascular surgery, peripheral vascular disease, diabetes, prior lower extremity vascular surgery, active lower extremity infection, any hypercoagulable condition (such as Factor V Leiden, or Protein C and S deficiency), pregnancy, *deep venous thrombosis, and pulmonary embolism*, or any condition you would want us to know.

13.4 Consent Process: Revised Common Rule, Section 219.116: General requirements for informed consent, whether written or oral, are set forth in this paragraph and apply to consent obtained in accordance with the requirements set forth in paragraphs (b) through (d) of this section. Broad consent may be obtained in lieu of informed consent obtained in accordance with paragraphs (b) and (c) of this section only with respect to the storage, maintenance, and secondary research uses of identifiable private information and identifiable biospecimens.

Are you requesting a waiver or alteration of informed consent?

Yes No

Please explain the consent process:

Study participants will receive informed consent. All informed consents will be conducted in person or via private virtual method. Participants will be provided with informed consent documents, explaining the study procedure, their ability to withdraw at any time, and compensation. The informed consent document for study participants will also explain the potential risks and discomfort they may experience during the

tourniquet application. Additionally, participants will be informed that one of the tourniquets used in this research study is an investigational device and it is for the present research use only.

Participants consent will be conducted in a private room or via a private virtual method.

Withdrawal from Study Participation:

Participation in this research study is completely voluntary. Participants may terminate their participation at any time. They can inform their decision to withdraw to the Principal Investigator, [name], verbally or in writing. In cases where participants withdraw verbally, the PI will document the decision in a timely manner.

13.5 DoDI 3216.02 requires an ombudsman to be present during recruitment briefings when research involves greater than minimal risk and recruitment of Service members occurs in a group setting. If applicable, you may nominate an individual to serve as the ombudsman.

- N/A
- Propose ombudsman

13.6 Withdrawal from Study Participation:

Explain the process for withdrawal and specify whether or not the subjects will be given the opportunity to withdraw their data their data/specimens in the event they wish to withdraw from the study

Participation in this research study is completely voluntary. Participants may terminate their participation at any time. They can inform their decision to withdraw to the Principal Investigator, [name], verbally or in writing. In cases where participants withdraw verbally, the PI will document the decision in a timely manner.

